4.6 Exploratory Analyses

- **Differential Impact of Confidence Signals:** We will compare diagnostic scores for vignettes receiving Red Signal (flawed) versus Orange Signal versus Green Signal by group.

- **Chronometric Analysis of System 2 Engagement:** Using timestamps, we will compare time spent on Red Signal versus Orange Signal vignettes within the Treatment group. Longer durations on Red Signal vignettes would indicate deeper System 2 processing.
- **Physician-Case Specialty Match:** Exploratory analysis will test whether automation bias is lower when a vignette matches the physician's specialty, independent of AI accuracy or signal type.

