Participants will be randomly assigned to control or treatment arms. Both groups will evaluate six clinical vignettes accompanied by LLM-generated recommendations, three of which contain deliberately introduced errors that are subtle yet clinically significant. LLM consultation will be discretionary, physicians will choose whether to view ChatGPT recommendations for each case.

The control arm will receive these recommendations without additional context. The treatment arm will receive a behavioral nudge intervention leveraging complementary cognitive mechanisms: (1) an anchoring cue displaying ChatGPT's average diagnostic reasoning accuracy on standard medical datasets before evaluation begins, establishing realistic performance expectations, and (2) a selective attention cue enabling deeper System 2 engagement through color-coded confidence signals when participants view ChatGPT recommendations. These confidence signals are generated through ensemble assessment: three independent state-of-the-art LLMs (Claude Sonnet 4.5, Gemini 2.5 Pro Thinking, and GPT-5.1) each provide confidence ratings for the recommendation, and the mean confidence determines the signal color. Multi-model aggregation mitigates the systematic overconfidence of single-model confidence reports, yielding more robust uncertainty estimates. Red signals indicate mean confidence below ChatGPT's baseline accuracy on medical benchmarks, prompting heightened critical scrutiny. Orange signals indicate above-baseline but less than 100% confidence, deliberately using orange rather than yellow to prevent complacency. Green signals indicate high ensemble confidence ($= 100\%$), though standard AI safety warnings apply (e.g., "AI may make mistakes. Always double-check.").

Clinical vignettes will be randomly sequenced to prevent pattern detection. By comparing diagnostic accuracy scores between arms, we will quantify the degree of automation bias in the control group and assess whether the behavioral nudge intervention reduces uncritical acceptance of erroneous AI-generated recommendations in the treatment group. This design enables

us to isolate both the magnitude of automation bias and the causal impact of transparency-based interventions on physician decision-making.

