1.2 Hypotheses

- **Primary Hypothesis (H1):** Physicians receiving the behavioral nudge intervention (baseline accuracy information and case-specific color-coded confidence signals) will demonstrate significantly higher diagnostic reasoning scores when evaluating clinical vignettes with deliberately flawed LLM recommendations compared to physicians receiving the same LLM recommendations without the nudge.
- **Secondary Hypotheses:**
 - **H2:** Physicians with less clinical experience will exhibit greater baseline automation bias and show larger treatment effects from the nudge intervention compared to more experienced clinicians.
 - **H3:** The intervention will demonstrate greater effectiveness for red-signal (below-baseline) versus orange-signal (above-baseline) recommendations.

2 Methods

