 - **Orange Signal:** Displayed when the ensemble confidence exceeds the established baseline average but remains below 100%. The choice of orange (vs. yellow) is a deliberate nudge to prevent automation bias and maintain clinical scrutiny.
 - **Green Signal:** Displayed when the ensemble reaches a consensus of 100% confidence. Standard caution will apply (e.g., “AI may make mistakes. Always double-check.”) to guard against over-reliance.

Randomization: Participants will be randomly assigned to either the intervention or control arm in a 1:1 ratio using a computer-generated random number sequence.

Blinding: Outcome assessors (those scoring the diagnostic reasoning performance) will be blinded to the participants’ group assignments. Participants will be blinded to the study’s specific hypothesis regarding automation bias but will be informed they are evaluating LLM diagnostic assistance tools.

Measuring change in automation bias: The primary measure of the change in automation bias will be the mean difference in diagnostic reasoning accuracy scores between the treatment and control arms. A positive difference favoring the treatment arm will indicate the reduction in automation bias attributable to the nudge.

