2.4 Clinical Vignettes & LLM Recommendations

Participants will evaluate six clinical vignettes specifically designed to measure automation bias. These vignettes will:

- Be based on modified real cases.
- Represent a range of diagnostic complexity across common medical specialties.
- Avoid overly simplistic or extremely rare conditions.
- Follow a standardized format, including:
 - Chief complaint and history of present illness.
 - Relevant past medical, social, and family history.
 - Physical examination findings.
 - Initial laboratory results.
- Include three clinical vignettes whose LLM recommendations contain deliberately introduced clinical reasoning errors and three with accurate recommendations, presented in randomized order. A panel of three licensed physicians will design these errors to be subtle yet clinically significant and detectable by trained clinicians.

- For every vignette, the LLM's recommendations will be pre-generated and fixed. This ensures all participants see identical recommendations for each vignette, the same error in flawed cases and the same correct reasoning in accurate cases, eliminating variance from real-time model variability.

Vignette Selection and Validation:

- A pool of 10 potential vignettes will be created and reviewed by an independent panel of three experienced medical doctors for:
 - Clinical accuracy and realism.
 - Appropriateness of difficulty level.
 - Clarity and completeness of information.
 - In flawed vignettes: subtlety and clinical significance of the introduced errors (errors should be detectable by competent physicians but not immediately obvious).
- Six vignettes will be selected based on the panel's ratings and feedback, aiming for a balanced representation of medical specialties and diagnostic challenges.
- For intervention arm participants, LLM output will be pre-generated and standardized for each vignette to ensure consistency in the presentation of correct or flawed information.

Vignette Completion:

- Each participant will complete all six vignettes in a single, proctored, approximately 75-minute session.
- The order of vignettes will be randomized for each participant to control for order effects and prevent pattern recognition.

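### The only score analysis for H3 equates red with flawed, so a larger nudge effect on red vignettes may not be attributable to the colour rather than to the presence of an error

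*Combined protocol and SAP*

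**What the plan says.** - **Hypothesis.** Section 1.2 lists H3 as secondary: "The intervention will demonstrate greater effectiveness for red-signal (below-baseline) versus orange-signal (above-baseline) recommendations".
- **Analysis.** H3 does not appear in the secondary or subgroup analyses (4.3, 4.4). The only score comparison by colour is in section 4.6, Exploratory Analyses: "We will compare diagnostic scores for vignettes receiving Red Signal (flawed) versus Orange Signal versus Green Signal by group". No model, contrast or adjustment for flaw status is given. A second item in 4.6 compares time on red and orange vignettes within the treatment group only, and would read longer red times as deeper deliberate processing.
- **How colour is set.** In the Introduction, "the mean confidence determines the signal color", and "Red signals indicate mean confidence below ChatGPT's baseline accuracy on medical benchmarks, prompting heightened critical scrutiny". Section 2.1 shows orange when confidence "exceeds the established baseline average but remains below 100" per cent. Green needs 100%.
- **How flaw status is set.** Under section 2.4 the vignettes will "Include three clinical vignettes whose LLM recommendations contain deliberately introduced clinical reasoning errors and three with accurate recommendations, presented in randomized order". A panel of physicians designs the errors, and each vignette has one fixed recommendation.
- **How vignettes are chosen.** Six of ten are taken on panel ratings and feedback, "aiming for a balanced representation of medical specialties and diagnostic challenges". Colour is not a criterion, and no number of vignettes per colour is set.

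**The concern.** Colour and flaw status are two separate properties of a vignette, fixed by different processes, and the analysis line treats them as one. A nudge against automation bias has an error to help catch only where the recommendation is flawed. If the red vignettes are the flawed ones, a larger effect on red is expected even if the colour does nothing. A positive H3 could then be reported as evidence that the red cue works better than the orange one, which the data could not show. If the two properties do not line up, the label in 4.6 misdescribes the groups, and nobody knows in advance how many vignettes each group holds.

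**Working it through.** **1. The plan's own figure.** Section 2.3 gives power for the main comparison only: 8 points, SD 16.2, ICC 0.05–0.15, 4 cases each, 25 per arm. Reading the SD as per case:
- design effect = 1 + (4 − 1) × ICC = 1.15 to 1.45
- effective cases per arm = 25 × 4 / design effect = 87.0 to 69.0
- SE = 16.2 × √(2/n) = 2.46 to 2.76
- power = Φ(8/SE − 1.96) = 0.90 to 0.83

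This agrees with the stated figure of at least 80%, which is not in dispute. No figure is given for H3.

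**2. Red = flawed, orange = accurate (three each).** Take a model with intercept, arm, red, flawed, arm × red and arm × flawed. The red and flawed columns are identical, and so are their products with arm. The design has 6 columns and rank 4. The estimated contrast is (nudge effect on flawed) − (nudge effect on accurate), whatever it is called. The control arm sees the same vignettes without signals, so plain case difficulty cancels; the presence of an error does not.

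Illustration, with assumed effects: the nudge adds 12 points on every flawed vignette and 0 on every accurate one, regardless of colour. The red-minus-orange contrast is 12 − 0 = 12 points, although the colour effect is 0.

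**3. Colours do not line up.** With, say, two red and one orange among the flawed, and one red and two orange among the accurate, the rank is 6 of 6 and arm × red is separable from arm × flawed. Separation is therefore possible, but nothing in 2.4 secures it.

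**4. How far it is left to chance.** The documents give no confidence values and no baseline cutoff, so the probabilities here are assumptions, with independent vignettes.
- Both colours among the three flawed, each red with probability p and no green: 1 − p³ − (1 − p)³ = 3p(1 − p). This is 75% at p = 0.5, 48% at p = 0.8 or 0.2, and 27% at p = 0.9 or 0.1.
- No red or no orange among all six, with probabilities r (red) and o (orange): (1 − r)⁶ + (1 − o)⁶ − (1 − r − o)⁶. This is 3% at 0.5/0.5 and 53% at 0.1/0.8.
- Green needs a mean of exactly 100%, so all three models must report 100%. That group may be empty.

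**5. Precision of arm × colour.** SE = 16.2 × √(1 − ICC) × √[(2/25)(1/a + 1/b)] for a red and b orange vignettes, assuming the nudge effect does not otherwise vary by vignette. Power is for an assumed 8-point difference in nudge effect, two-sided 0.05; ranges run over ICC 0.05 to 0.15.

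| Red / orange | SE | Power for 8 points | Difference with 80% power |
|---|---|---|---|
| 3 / 3 | 3.65–3.45 | 59–64% | 10.2–9.7 |
| 1 / 2 or 2 / 1 | 5.47–5.17 | 31–34% | 15.3–14.5 |
| 1 / 1 | 6.32–5.97 | 24–27% | 17.7–16.7 |

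The 3/3 row is best for precision, but if it arises as in step 2 it says nothing specific to colour.

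**6. Timing.** The red-versus-orange time comparison uses the treatment arm alone. It carries the same confounding with flaw status and, unlike the scores, no control-arm contrast to remove differences between the cases themselves.

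**The case against.** H3 as worded concerns where the nudge works, not whether colour is the cause. The comparison is by group, so an arm-by-colour contrast can be computed whenever at least one red and one orange vignette exist, and it answers H3 in that literal sense. The analysis is exploratory. The label may mean only that every red vignette is flawed, which leaves room for orange flawed ones.

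Most of this stands, and it rules out three stronger readings that a reader might infer:
- *That H3 is untestable or goes unanswered either way.* It does not. Mixed colours among the flawed vignettes would be the layout that allows colour to be separated from error.
- *That the red group will be nearly empty because LLMs are overconfident.* Section 2.1.1 gives overconfidence as the reason for using an ensemble instead of one model's self-report. Without confidence values or a cutoff, an empty red group is conjecture.
- *That vignettes must be re-selected by colour.* Requiring an orange flawed vignette would change the case set for H1 and place an above-baseline signal on a wrong recommendation by design. Within three flawed vignettes, colour would still rest on one case against two, and so be mixed with how detectable each error is.

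What the objection does not remove is the causal reading. The cue is described as acting through its colour, the timing analysis interprets colour as mechanism, and the plan nowhere says that a red-versus-orange difference will not be read as a colour effect.

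**Conclusion.** The concern holds as a limit on what may be concluded from H3. If colour and flaw status coincide, they are fully aliased (rank 4 of 6), and no later analysis of the fixed vignettes can attribute a larger red effect to the colour. If they do not coincide, the label in 4.6 is wrong and the group sizes are unknown until the signals are computed. Even where colour can be separated from error, a contrast within the flawed vignettes has about 31–34% power for 8 points, and less if the nudge effect varies between vignettes.

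The aliasing follows from the documents' own definitions once red is equated with flawed. The 12-point illustration, the colour probabilities and the 8-point interaction are assumptions. The contrast, model and significance level for H1 are not affected.

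**What to change.** 1. In 4.6, delete the bracketed label after red.
2. Compute the ensemble signal for the candidate vignettes before the set is locked, and report the colour by flaw-status table.
3. Where both colours occur among vignettes of the same flaw status, estimate arm × colour with arm × flaw status in the model, or within the flawed vignettes alone. Report it as an estimate with its interval.
4. Where colour and flaw status are fully aliased, restate H3 as flawed versus accurate and make no claim about colour.
5. Compare the red-versus-orange time difference with the control arm's time on the same vignettes, under the same limit on colour claims.
6. Drop any colour that no vignette receives.

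Colour may be used to choose between otherwise equally rated vignettes, but this is optional because of its effect on the H1 case set.

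Cost: 10 candidates × 3 models = 30 queries, and revised wording in 1.2 and 4.6. The downside is that H3 becomes a descriptive result of low precision.

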2.1 Study Design

This study will be a single-blind, randomized controlled trial with two parallel arms. Participants will be randomly assigned in a 1:1 ratio to the intervention arm or to the control arm. To control for variability in user prompting skills, participants will not interact directly with a live LLM chat interface. Instead, they will use a custom-built web platform that displays the clinical vignette and provides access to pre-generated LLM recommendations.

- **Control Arm:** Participants will evaluate six clinical vignettes (three with deliberately flawed diagnostic information and three with correct information). Through the study platform, they will be able to view “LLM Diagnostic Recommendations” generated by ChatGPT. These recommendations will be presented in a standard, neutral text format without additional context or nudge.
- **Intervention Arm:** Participants will evaluate the same six clinical vignettes using the same web platform, but with a behavioral nudge embedded directly within the LLM suggestion interface. Upon expanding the LLM recommendation panel for any vignette, participants will be presented with two synchronized cognitive cues:

1. **Anchoring Cue:** Displayed at the top of the panel, this visual cue presents ChatGPT’s baseline diagnostic accuracy on standard medical datasets (e.g., Medbullets). This serves to explicitly anchor expectations to the model’s realistic performance level, preventing both excessive skepticism and uncritical acceptance, before the participant reads the specific recommendation.
2. **Selective Attention Cue:** Below the baseline accuracy information, each case-specific LLM recommendation will be displayed alongside a color-coded signal reflecting the ensemble confidence for that particular recommendation. This score is derived from a consensus evaluation by three independent state-of-the-art LLMs (e.g., Claude 4.5 Sonnet, Gemini 2.5 Pro Thinking, and GPT-5.1) to mitigate single-model miscalibration:
 - **Red Signal:** Displayed when the ensemble’s mean confidence falls below ChatGPT’s established baseline accuracy, signaling a high-uncertainty case that requires deeper critical evaluation and indicating “*The LLM is less sure about this case than it usually is*”.

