2.5 Data Collection

2.5.1 Session Protocol

- Participants will complete the study under proctored conditions (in person or via secure video conferencing).
- Participants will complete a brief baseline questionnaire collecting demographic information (gender, specialty, years of experience), technology proficiency, and prior LLM experience.
- Participants will receive instructions specific to their assigned group (intervention or control).
- Participants will evaluate clinical vignettes one at a time.
- For each vignette, participants will provide:
 1. Their top three differential diagnoses.
 2. Supporting and opposing factors for each differential diagnosis (clinical findings, test results, etc.).
 3. Their most likely final diagnosis.
 4. Recommended next steps in the diagnostic workup (e.g., further tests, consultations).
- Participants will record all responses using a standardized electronic form.
- Time spent per vignette will be automatically tracked.
- For each vignette, a binary indicator will record whether the participant accessed the LLM recommendations (1 = viewed; 0 = not viewed).

3 Outcome Measures

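### The timing analysis compares red with orange vignettes in the treatment arm only, so longer red times cannot be told apart from slower cases, and the control-arm times are left unused

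*Combined protocol and SAP*

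**What the plan says.** The timing bullet in Section 4.6 reads: "Using timestamps, we will compare time spent on Red Signal versus Orange Signal vignettes within the Treatment group". The interpretation follows directly: "Longer durations on Red Signal vignettes would indicate deeper System 2 processing". No test, model or vignette adjustment is given for this analysis. The vignette random effect in Sections 4.2 and 4.3 is stated for the score outcomes only.

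Four other places matter:

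- Section 2.4, on the fixed recommendations: "This ensures all participants see identical recommendations for each vignette, the same error in flawed cases and the same correct reasoning in accurate cases".
- Section 2.1, on the signal: "each case-specific LLM recommendation will be displayed alongside a color-coded signal reflecting the ensemble confidence for that particular recommendation".
- Section 2.1, on the intervention arm's cases, compared with the control arm's: "Participants will evaluate the same six clinical vignettes using the same web platform".
- Section 2.5.1, without restriction to one arm: "Time spent per vignette will be automatically tracked".

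Opening the panel is optional (Section 1: "LLM consultation will be discretionary, physicians will choose whether to view ChatGPT recommendations for each case"), and Section 2.5.1 records it: "a binary indicator will record whether the participant accessed the LLM recommendations". The neighbouring score comparison in Section 4.6 is made by group. The timing comparison is not.

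**The concern.** The red and the orange vignettes are different cases with different recommendations. Section 2.4 wants the cases to span a range of complexity and specialties, and Section 4.2 expects difficulty to vary. Section 4.6 also describes red vignettes as flawed, so the contrast may carry the effect of a planted error as well. Any of these can change reading and thinking time with no signal on the screen. Randomising the order of the vignettes removes order effects, not case effects.

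This bullet is the plan's only stated analysis of the System 2 mechanism. Under its rule the trial could report that the nudge triggers deeper processing when it does nothing, or miss a real slow-down because the red cases happen to be quick. The documents do not say which way the case differences run.

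**Working it through.** **1. What the contrast estimates.** Let the mean log time on vignette *v* be β_v in the control arm and β_v + δ + γ·red_v in the treatment arm. Here γ is the extra slow-down that the nudge causes on red compared with orange. The red-minus-orange differences are:

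- Treatment arm: D_T = γ + (mean β of red − mean β of orange)
- Control arm: D_C = (mean β of red − mean β of orange)
- Difference: D_T − D_C = γ

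The planned analysis uses D_T alone, which cannot separate γ from the case gap. The control arm supplies D_C.

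**2. Inputs for the size.** From the documents: 25 per arm (Section 2.3) and six vignettes (Section 2.4). The plan gives no figure for timing, so there is none to reproduce. Assumed: three red and three orange vignettes, t tests at two-sided 5%, residual log-time SD σ = 0.3 (range 0.2 to 0.5), vignette log-time SD τ. Differences between participants cancel within person.

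- SE of D_T = σ√(1/3 + 1/3)/√25 = 0.3 × 0.8165/5 = 0.0490
- SE of D_T − D_C = √2 × 0.0490 = 0.0693, a ratio of 1.41

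**3. No nudge effect, cases differ at random.** The case gap has SD τ√(2/3). The paired t statistic then behaves as a t on 24 df multiplied by k = √(1 + (τ√(2/3)/0.0490)²), so the chance of a false *red longer* result is P(t₂₄ > 2.064/k).

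| τ | k | False *red longer* |
|---|---|---|
| 0.05 | 1.302 | 6.3% |
| 0.10 | 1.944 | 14.9% |
| 0.20 | 3.480 | 27.9% |
| 0.30 | 5.099 | 34.5% |

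Nominal is 2.5%; rejections in either direction are double these. At τ = 0.10 the rate is 22.5%, 14.9%, 10.5% and 7.9% for σ = 0.2, 0.3, 0.4 and 0.5.

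**4. No nudge effect, red cases 10% slower in both arms.** The noncentrality is ln(1.1)/0.0490 = 0.0953/0.0490 = 1.946. On 24 df this gives *red longer* in 46% of trials. For σ = 0.2, 0.4 and 0.5 the same formula gives 80%, 29% and 20%.

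**5. A real 20% slow-down on red, red cases 10% quicker.**

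- Treatment arm only: ln(1.2) + ln(0.9) = 0.1823 − 0.1054 = 0.0770; 0.0770/0.0490 = 1.571; power 33%.
- Two-arm contrast: 0.1823/0.0693 = 2.632; on 48 df, power 73%.

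**6. Two-arm contrast with no nudge effect.** The case gap cancels, so *red longer* stays at the nominal 2.5%, provided the nudge effect is the same on every vignette. Simulation of 20,000 trials gave 2.3% to 2.8%.

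**The case against.** The strongest reply is that the rates in step 3 belong to a test the plan does not name. Section 4.6 says only that times will be compared. If the analysts treated vignettes as random, as they do for the scores, a vignette-level test on 4 df in the treatment arm alone would hold 2.5% against random case differences. That is correct, and step 3 should be read with that condition. It does not rescue the design: if red cases as a class are 10% slower, the noncentrality of 1.946 against a critical value of 2.776 on 4 df still gives *red longer* in 32% of trials with no other vignette variation, and 12% at τ = 0.10. Only the control arm removes a systematic gap.

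Second, the two-arm contrast is itself vulnerable. If the nudge effect varies by vignette with log SD 0.05, 0.10 or 0.20, the contrast without a treatment-by-vignette term rejects in 9%, 20% and 43% of null trials. This stands, and it limits what can be claimed beyond these six vignettes.

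Third, the analysis is exploratory, time is neither a primary nor a secondary outcome, and no numbered hypothesis concerns it. This also stands and limits the weight of the point. Exploratory status does not make a pre-stated interpretation valid, however.

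**Conclusion.** The concern holds. That colour is fixed to the vignette is an inference from Sections 2.1 and 2.4, but a firm one, and no section uses the control-arm times. The design argument needs no simulation. The rates show only that modest case differences are enough to mislead. They rest on assumed variances, an assumed three-to-three colour split and, for step 3, a test without vignette effects.

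The primary analysis and its conclusion are unaffected. What fails is the planned statement about mechanism. This should be corrected before the data are analysed; it does not threaten the trial.

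**What to change.** Replace the timing bullet in Section 4.6 with a model of log time in both arms: participant random intercept, vignette effects (which absorb the main effect of colour), treatment, and treatment-by-colour interaction. Analyse all participants as randomised, whether or not they opened the panel, and report panel viewing by arm and colour separately.

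Replace the System 2 sentence with: *A positive interaction means that the nudge lengthened time on red more than on orange vignettes; this is consistent with deeper processing but does not prove it.* Label the analysis exploratory. State that it concerns the whole nudge on these six vignettes and does not isolate colour from flawed content, the anchoring cue or time spent reading the red message. Either restrict the conclusion to these vignettes or add a treatment-by-vignette random term, and say which in advance.

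Two small wording points in the same section: write the score comparison that serves H3 as a treatment-by-colour interaction, and reconcile the description of red as flawed with its confidence-based definition in Section 2.1, with a cross-tabulation of colour against error status.

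**Cost.** SAP wording only; the times and viewing indicator are already collected.

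- The standard error is 1.41 times larger. Power for a 20% slow-down is 97%, 73%, 49% and 34% at σ = 0.2, 0.3, 0.4 and 0.5.
- At σ = 0.3, power falls to 56% with two red and two orange vignettes, and to 54% (simulated) if only 80% of panels are opened.
- A vignette-level test that allows the nudge effect to vary holds 5%. Its power is 52% if there is no such variation and 41%, 26% and about 12% at log SD 0.05, 0.10 and 0.20.
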